Therapy Modes for Helix Ventilator

The device that is being evaluated in this study can provide many different modes of therapy in both pressure support and volume controlled ventilation.

The following is a list of modes that may be provided with these devices, dependent on patient prescriptions:

- Continuous Positive Airway Pressure (CPAP) with optional C-Flex
- Spontaneous Pressure Support (S) with optional Bi-Flex
- Spontaneous/Timed Pressure Support (S/T)
- Pressure Control Pressure Support (PC)
- Timed Pressure Support (T)
- Averaged Volume Assured Pressure Support (AVAPS) in conjunction with the modes listed above (S, S/T, PC, T)
- Volume Control Ventilation (CV)
- Volume Assist Control (AC)
- Synchronous Intermittent Mandatory Ventilation (SIMV)
- Pressure Control SIMV (PC SIMV)
- Pressure Regulated Volume Control (PRVC)

Target Patient Population

The patient population is extremely varied. The patient's age will vary from infant ($\geq 5\text{kg}$) to adult. The medical condition of the patient population ranges from critically ill acute respiratory conditions to pre-existing or developing chronic conditions. Patients treated with the Helix ventilator may suffer from diseases or injuries requiring invasive or non-invasive ventilation. Many of these diseases result in respiratory failure, which can be classified as acute or chronic. Acute respiratory failure is typically treated in a hospital ICU or sub-acute hospital, while chronic respiratory failure is treated at home or in a long term care facility. Specific examples of respiratory failure include, but are not limited to:

- Neuromuscular diseases leading to respiratory failure: Amyotrophic Lateral Sclerosis (ALS), Spinal Muscular Atrophy (SMA), Duchenne Muscular Dystrophy (DMD)

Engineering Evaluation of the Helix Family of Ventilators

Confidential

HRC-17067-HCPED-CC Version: 2.0, 26-Oct-2018

Page 13 of 21

- Chronic Obstructive Pulmonary Disease (COPD)
- Asthma
- Spinal cord injuries
- Thoracic cage deformities
- Pneumonia originating from infectious disease such as influenza
- Pulmonary edema (symptom of congestive heart failure)
- Trauma leading to Acute Lung Injury (ALI)
- Acute Respiratory Distress Syndrome (ARDS)

II. Study Objective

The objective of this Engineering study is to verify the overall performance and controls of the Helix Ventilator.

Specific Aims

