1. To collect and compare pressure and flow data between the participant's current therapy device and the Helix ventilator in either invasive or non-invasive ventilation. Pressure and flow waveform data will be evaluated to assess ventilator performance such as delivered pressure such as volume control accuracy, patient synchrony (triggering/cycling), and measured/calculated parameter accuracy.
2. To evaluate the therapy delivery using alternate circuit types, such as mouthpiece ventilation (MPV) or passive dual limb
3. To obtain participant feedback regarding the comfort of the therapy delivery.
4. To obtain caregiver feedback related to the usability of the study device
5. To evaluate the alarm functionality of the study device.
6. To compare the device's Spirometry measurement while it is operating on standard and alternative circuits, (Tidal Volume, breath rate, Peak flows) against a control measurement device

III. Subject Selection

Participants will be recruited from Boston Children's Health Physician's Group. Initial contact will be made by the participant's physician, or by his/her designee

Engineering Evaluation of the Helix Family of Ventilators

Confidential

HRC-17067-HCPED-CC Version: 2.0, 26-Oct-2018

Page 14 of 21

Inclusion Criteria

Participants who are currently using mechanical ventilation (> 1 month at time of study participation) as part of medical care and have demonstrated a clinically acceptable response to this therapy and meet the following inclusion criteria:

1. Weight \geq 5Kg;
2. Any medical condition requiring mechanical ventilation through nasal/facial mask, mouthpiece or tracheostomy
3. Any medical condition requiring mechanical ventilation for > 1 month

Exclusion Criteria

1. Participants intubated with an endotracheal tube
2. Clinically unstable, i.e.,
 - a. Acute Respiratory Failure
 - b. Participants with refractory hypotension (defined as systolic blood pressure less than 90 mm Hg despite inotropic agents)
 - c. Uncontrolled cardiac ischemia or arrhythmias
 - d. Any participant determined as inappropriate for the study by the Principal Investigator
3. Patients suffering from metastatic or terminal cancer
4. Currently employed by a manufacturer of respiratory products or family member employed by a manufacturer of respiratory products
Patient of surrogate is unable to provide informed consent

IV. Study Design

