This clinical study is a non-randomized, single site, single-arm engineering clinical comparison study. The study is designed to collect and compare device parameters from the patient's current ventilator compared to the Helix ventilator.

V. Participant Enrollment

Following initial contact by their physician or his/her surrogate, participants/surrogate will be informed that their participation is entirely voluntary and the decision to participate or not, will in no way affect their further evaluation or therapy. Subsequently, the participant or surrogate will be given a complete and thorough explanation of the benefits and risks or discomforts that may be anticipated with this study. Informed consent will be obtained prior to enrollment in the study.

Sample Size:

Up to thirty (30) participants will be recruited for this study.

Engineering Evaluation of the Helix Family of Ventilators

Confidential

HRC-17067-HCPED-CC Version: 2.0, 26-Oct-2018

Page 15 of 21

VI. Study Procedures

Following the completion of the informed consent, participants enrolled in this study will be asked to use their existing ventilator for up to 1 hour to collect pressure and flow data for comparison purposes against the Helix ventilator.

Participants will then be set up on the Helix Ventilatory System using the same mode of therapy as their current ventilator. Participants may receive mechanical ventilation using any patient circuit currently being designed for the Helix Ventilator (Passive, Active with PAP, Active with Flow, or dual limb). Patients currently using non-invasive ventilation may be asked to use a mouth piece in lieu of a mask interface. While using the study device, therapy setting may be altered by the physician or his/her surrogate while maintaining the ventilator needs of the patient. For e.g., a patient currently prescribed an SIMV mode may temporarily be switched to a pressure control mode to assess patient synchrony and ventilator performance.

Once the participant is set-up, he/she will be asked to use the ventilator for up to 4 hours. During this time, Philips Respiration engineers will be collecting data through several mechanisms: 1) Helix SD Card, 2) NICO Monitoring System, and / or 3) External data collection device (ex. laptop). The study staff may ask the participant's opinions on the comfort of the therapy delivery. There will be no invasive monitoring as part of this study.

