Trends Analysis

The aim of this Engineering study is to verify the performance and controls of the Helix Ventilator. If formal significance testing is required, the endpoints will be compared between the device versions, including device hardware, software,

For continuous data, within-subject comparisons between two iterations will be performed using paired t-tests or the non-parametric Wilcoxon Signed-Ranks test, depending on the distribution of the data.

Within-subject comparisons across three or more iterations will be done using Repeated-Measures Analysis of Variance (RMANOVA) or the non-parametric Friedman Test. For participants who only try one iteration throughout the trial, between-subjects comparisons across two iterations will be done using independent-samples t-tests or the Mann Whitney test. If between-subjects comparisons are made across

Engineering Evaluation of the Helix Family of Ventilators

Confidential

HRC-17067-HCPED-CC Version: 2.0, 26-Oct-2018

Page 17 of 21

three or more iterations, ANOVA or the Kruskal-Wallis test will be employed. Post-hoc pairwise comparisons will include an appropriate alpha adjustment.

If formal analysis of categorical data is required, methods such as the Fisher's Exact or Chi Squared Test will be used for between-subjects comparisons, and the McNemar Test or Cochran's Q will be used for within-subject comparisons.

All tests will be conducted at a significance level of $p < 0.05$.

Treatment Compliance

It is expected that the drop-out rate will be low as the study is an engineering trial.

Safety Analysis

Safety evaluations will be performed by recording clinical adverse events at the time originally reported, and they will be followed at each visit thereafter until resolution. Adverse events will be provided in data listings.

Interim Analysis

There is no interim analysis planned for this study.

VIII. Risks and Discomforts

The risks of providing ventilatory support with the study device are no greater than the risks encountered with other ventilatory support devices.

The devices that will be used by the subject have been tested to ensure safety. Should the device not perform as designed, ventilation could increase and decrease more than desired. This effect could be uncomfortable. Should any problems be identified, the respiratory therapist will remove the study device and resume ventilatory support with the participant's current device.

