The Helix ventilator has similar modalities to the Trilogy ventilator, which has FDA clearance. The key differences between the Helix Ventilator (study device) and previously cleared Trilogy devices are that the Helix device has improved algorithms, controls, and features to enhance the therapy delivery. Additionally Helix has an updated hardware platform which has been adequately tested to ensure that the device specifications are met. The improved algorithms and controls have been adequately tested to ensure that the delivery of therapy meets the device specifications.

Respironics believes that this patient study is a low risk study that does not require an IDE because of the following:

- The predicate devices, Trilogy Family of Ventilators, have been cleared by FDA:

Engineering Evaluation of the Helix Family of Ventilators

Confidential

HRC-17067-HCPED-CC Version: 2.0, 26-Oct-2018

Page 18 of 21

- K083526 Trilogy 100 Ventilator
- K093416 Trilogy 200 Ventilator
- K093905 Trilogy 202 Ventilator

- The study device uses existing modes of therapy, therapy features and algorithms that have been previously cleared by FDA
- This patient study is recruiting stable, mechanically ventilated participants and will be conducted in a controlled, monitored environment
- The study will be supervised at all times by a respiratory therapist and/or other qualified site clinical staff.

Confidentiality:

Participants will be instructed to contact Philips staff with any questions and concerns related to the device use or the study in general. All information recorded by the study team will be study ID number.

Privacy rules and requirements according to federal and state governing regulations will be implemented. All the information collected as part of this study will be kept confidential. All information collected for this study will be kept in a secured area or stored in a password protected computer if digital.

Confidentiality of data shall be observed by all parties involved at all times throughout the clinical study. All data shall be secured against unauthorized access.

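### The aim is to verify Helix performance, but Section VII has no acceptance limit, agreement analysis or confidence interval, and its conditional tests address a different question

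*Combined protocol and SAP*

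**What the plan says.** Section II sets the goal: "The objective of this Engineering study is to verify the overall performance and controls of the Helix Ventilator". The Trends Analysis part of Section VII repeats it: "The aim of this Engineering study is to verify the performance and controls of the Helix Ventilator".

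The quantities are named in the Specific Aims. Aim 1 compares pressure and flow between the participant's current device and Helix, to assess among other things "volume control accuracy, patient synchrony (triggering/cycling), and measured/calculated parameter accuracy". Aim 6 compares the device's spirometry "against a control measurement device". Section IV describes the same contrast: "The study is designed to collect and compare device parameters from the patient's current ventilator compared to the Helix ventilator".

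Section VII opens by saying that no formal analysis is planned. General Considerations lists means, SDs, medians and extremes for continuous variables, and counts with percentages for categorical ones. If formal testing proves necessary, Trends Analysis compares endpoints between device versions, using paired or independent t-tests, ANOVA, their rank-based counterparts and the usual categorical tests. It adds: "All tests will be conducted at a significance level of" p < 0.05.

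Device specifications appear only as something already checked. Section VIII says the algorithms and controls were "adequately tested to ensure that the delivery of therapy meets the device specifications"; Section I says much the same of the hardware. No specification values are given, and none is used as a criterion in this study.

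**The concern.** To verify accuracy is to show that error stays within a stated limit. That takes a limit, a reference and a statement of how precisely the error has been estimated. Section VII supplies no limit and no measure of precision, and it does not say how the reference named in Aim 6 enters the analysis.

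The tests held in reserve do not close the gap. A test of difference can show that two things differ. It cannot show that they agree, and it grows less able to flag a problem as participants become fewer. Nor are these tests aimed at the comparisons in Aims 1 and 6.

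What is at stake is the study's main conclusion. Followed as written, the plan gives tables from which a reader cannot tell whether performance was verified, was not verified, or was estimated too imprecisely to say.

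**Working it through.** **Nothing to reproduce.** The plan gives no effect size, SD, margin or power, and Section VII says no sample-size calculation was done.

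**Aims set against methods**

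| Question | Comparison needed | What Section VII offers |
|---|---|---|
| Aim 1 | Helix against current ventilator, same participant | Descriptive tables; tests named only for version against version |
| Aim 6 | Helix reading against control measurement | Descriptive tables; no limits of agreement, no tolerance |
| Verification (Sections II and VII) | Error against a stated limit | No limit, no CI, no decision rule |

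Every method named in Trends Analysis is a test of difference. A null result between two Helix versions would not speak to accuracy at any sample size, since both versions could be wrong by the same amount.

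**How a test of difference behaves if it is applied to paired data**

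Inputs from the plan: significance level 0.05; at most 30 participants (Sections V and VII); a goal of 30 completers, without replacement (Section VIII, Withdrawal Criteria).

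Assumptions, not in the plan: two-sided testing; a true shift of 0.5 SD of the paired differences; one observation per participant per condition; 10 pairs as an example of a smaller comparison.

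With n pairs and shift d in SD units, the paired t statistic has n − 1 degrees of freedom and noncentrality d√n. With F the noncentral t distribution function and c the 97.5% point of central t,

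P(non-significant) = F(c) − F(−c).

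The 95% CI half-width, in units of the sample SD of the differences, is c/√n.

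| n | c | d√n | P(non-significant) | CI half-width |
|---|---|---|---|---|
| 30 | 2.045 | 0.5 × 5.477 = 2.739 | 0.246 | 2.045/5.477 = 0.37 SD |
| 10 | 2.262 | 0.5 × 3.162 = 1.581 | 0.707 | 2.262/3.162 = 0.72 SD |

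At 30 pairs the test is not blind: it has 80% power for a shift of 0.53 SD and misses a shift of 0.8 SD about 1% of the time. With 10 pairs the shift needed for 80% power is 1.00 SD. With 5 pairs the smallest two-sided exact Wilcoxon signed-rank p-value is 2/2⁵ = 0.0625, so that test could never reach 0.05.

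**What a CI held against a limit would show**

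Assume a true mean error of zero and a limit of ±m SD (m is assumed, because no specification values are given). The 95% CI lies inside the limit when |mean| < h, where h = m − c·s/√n, s is the sample SD in units of the true SD, and h must be positive. Averaging 2Φ(h√n) − 1 over the distribution of s, with (n − 1)s² chi-squared on n − 1 degrees of freedom, gives:

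| Assumed limit | 30 pairs | 10 pairs |
|---|---|---|
| 0.5 SD | 51% | 2% |
| 0.75 SD | about 96% | 23% |

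With few participants, this approach tends to return inconclusive.

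**The case against.** The strongest reply is that this is an exploratory engineering study that says so. It plans no formal analysis, makes no sample-size claim and mentions testing only as a contingency. Sections I and VIII say that testing against specification has already been done, so formal verification may sit outside this protocol. On that view the word verify is loose drafting.

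Much of this stands. In particular, a reader might infer that a small sample passes by default because non-significance would be taken as verified. The documents do not support that. No section treats p ≥ 0.05 as a pass, and Section VII defines no pass rule of any kind. Nor is non-significance the only favourable result available: because the tests compare versions, a significant improvement from one iteration to the next would also be welcome. A reader might equally infer that the study is bound to be too small. The goal is 30 completers and drop-out is expected to be low, and at 30 pairs moderate to large shifts would usually be found. The 0.5 SD shift is illustrative; with no SD or tolerance in the documents, it may lie well inside or well outside specification.

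What does not stand is the idea that a descriptive plan needs no criterion. A table of means and SDs without a limit cannot verify anything either, and the aim is stated twice in those terms. Earlier testing to specification does not supply the criterion for data from participants.

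A further caution applies to the remedy. A CI for the mean error can lie inside a limit while individual participants fall outside it, so the CI should not be the sole rule.

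**Conclusion.** The concern holds in this form: the plan states a verification aim but no criterion by which to judge it, and its conditional tests do not match the comparisons in Aims 1 and 6. This follows from the text and rests on no assumption about sample size.

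The figures of 25% non-significant at 30 pairs and 71% at 10 show only why a null test result could not stand in for the missing criterion. They rest on the assumed 0.5 SD shift, two-sided testing and one observation per participant per condition. Section VI allows up to six sessions per participant, which would change the effective sample size. Thirty is a ceiling with no stated minimum, and comparisons between versions may draw on fewer pairs, but the documents do not say how many.

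**What to change.** In Section VII:

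- For each controlled or measured quantity that has a device accuracy specification, list the specification as the limit and fix it before analysis.
- Name the reference measurement. Section VI lists several means of data collection joined by and/or, so the plan should say which serves as the reference for which quantity.
- Report the error against the reference, and separately the paired difference from the current ventilator, as a mean with 95% CI and limits of agreement. Use a method that allows for repeated sessions per participant, such as a mixed model with a participant effect.
- Report the share of participants within the specification.
- Limit the word verified to quantities judged against a pre-stated limit, using both the CI and the within-limit share. Report as inconclusive where these do not settle the matter.
- State that p ≥ 0.05 is not evidence of agreement.
- Treat all other quantities, such as synchrony and comfort, as descriptive only.

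If no limits are adopted, reword the aim in Sections II and VII as descriptive.

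The cost is a little more analysis and the work of listing specification limits, which the sponsor should hold but which are not in the documents. No added participants are needed, and no added procedures where a reference reading is already recorded. The real downside is that some quantities may come out inconclusive, and possibly many if the limits are tight relative to the SD or few participants contribute.

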The engineering evaluations will take place at the Boston Children's Health Physician offices. The study investigators, respiratory therapist, and/or other qualified clinical staff, will be supervising and present for all study visits. Philips Respiration engineers will be present for observational purposes only. All study staff working on this trial will be trained to the protocol and device prior to beginning work.

Participants may be asked to participate in this data collection study up to six (6) times.

Study data collected for this study will be collected on paper or electronic source records. These records will include information regarding inclusion/exclusion, performed study procedures and questions regarding device use. Only those staff that have been delegated by the Principal Investigator will be able to enter or make changes to the data in the Case Report Forms.

Engineering Evaluation of the Helix Family of Ventilators

Confidential

HRC-17067-HCPED-CC Version: 2.0, 26-Oct-2018

Page 16 of 21

VII. Statistical Analysis

The purpose of this Engineering study is to collect engineering and subjective data on the Helix Ventilatory System and the patient's existing ventilator device for comparison purposes. Therefore, no formal analysis of the data is planned.

Determination of Sample Size

Up to 30 participants will be enrolled in the study. Since this is an engineering study to address issues which arise, no sample-size calculation was performed.

General Considerations

The primary analysis will be performed including all completed participants. Descriptive data tables will be provided for all variables of interest. Continuous data will be presented by mean, standard deviation, median, minimum, and maximum observation. Data will be presented in the untransformed and transformed format (if applicable) for each continuous variable. Categorical data will be presented as frequencies and percentages. All analyses will be conducted using either SAS® or SPSS® software.

Participant Disposition

Participant disposition, including the total number of participant's enrolled, completed, early terminations and withdrawals, will be presented overall and by software version. A listing will be provided with the reasons for discontinuation.

Demographics and Baseline Characteristics

Standard subject demographics (e.g., age and gender) and baseline characteristics will be summarized for all participants enrolled and for evaluable participants.

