The privacy of each subject and confidentiality of his/her information shall be preserved in reports and when publishing any data. Except when required by law, participants will not be identified by name, social security number, address, telephone number, or any other direct personal identifier in study records. For records disclosed outside the Philips Respiration, participants will be assigned a unique code number.

Results of the study related data, medical history, and information obtained from the questionnaires and device data will be reported and received by Philips Respiration. Philips Respiration will use participant study data for research purposes to support scientific and marketing objectives described in this protocol.

In addition, participant records may be reviewed in order to meet federal and state regulations. Reviewers may include representatives from the FDA or similar government authorities in other countries where the device is being used, and Philips Respiration for the purposes of the following side effects, and to gather additional information related to the study, and the Institutional Review Board (IRB). Participant permission for review of confidential information is granted by signing the associated informed consent. Philips Respiration will ensure that it follows all applicable state and federal data protection regulations.

Withdrawal Criteria:

The term “discontinuation” refers to the participant’s premature withdrawal from the study prior to completing all procedures. Participants may be discontinued from the study for any of the following reasons:

Engineering Evaluation of the Helix Family of Ventilators

Confidential

HRC-17067-HCPED-CC Version: 2.0, 26-Oct-2018

Page 19 of 21

- If in the investigator's judgement, continuation in the study may prove harmful to the participant. Such a decision may be precipitated by adverse events, including fever, nausea, rash, changes in vital signs, or the development of a new medical condition. The investigator will be solely responsible for making medical/safety decisions regarding the participant's continued participation in the study.
- Noncompliance;
- At the request of the participant.

The study team will document whether or not each participant completed the study. If, for any participant, study treatment or assessments were discontinued, the reason will be recorded.

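### If version comparisons are tested, the between-subjects set is chosen by who did not try a second version; using each participant's first Helix exposure avoids that selection

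*Combined protocol and SAP*

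**What the plan says.** Section VII opens by ruling out formal inference: "Therefore, no formal analysis of the data is planned". Trends Analysis then gives contingent rules: "If formal significance testing is required, the endpoints will be compared between the device versions".

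Two routes follow, depending on how many versions a participant tried:

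- Participants with two versions: "within-subject comparisons between two iterations will be performed using paired t-tests or the non-parametric Wilcoxon Signed-Ranks test". Repeated-measures ANOVA or Friedman applies for three or more.
- Participants with one version: "For participants who only try one iteration throughout the trial, between-subjects comparisons across two iterations will be done using independent-samples t-tests", or Mann-Whitney. ANOVA or Kruskal-Wallis applies for three or more versions.

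The level is fixed too: "All tests will be conducted at a significance level of" p < 0.05.

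Three other places bear on who ends up with only one version:

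- Section VI, on return visits: "Participants may be asked to participate in this data collection study up to six (6) times". No rule says who is asked back or on which version.
- Section VIII, Withdrawal Criteria, allows discontinuation for noncompliance, at the participant's request, or on this ground: "If in the investigator's judgement, continuation in the study may prove harmful to the participant".
- Section IV, on allocation: "This clinical study is a non-randomized, single site, single-arm engineering clinical comparison study".

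The analysis population is unsettled. General Considerations in Section VII bases the primary analysis on completed participants. Withdrawal Criteria in Section VIII keeps all collected data unless the participant objects.

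**The concern.** The between-subjects set is defined by a post-enrolment event. Someone tested on one version belongs to it only if they do not later try another, and the plan allows that to happen for reasons that may relate to the outcome. Comfort and patient-ventilator synchrony are among the study aims, and poor results on either could plausibly lead to withdrawal. Because the study exists to address issues that arise, poor results could equally make re-invitation more likely. The sign of any bias is therefore not fixed.

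If the tests were run, a difference between versions could reflect who failed to return and not what changed in the device. Planned disposition by software version would show withdrawals, but it would not correct the comparison and would not show people who were simply never asked back. Even when return has nothing to do with outcome, the rule discards usable first-exposure records.

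**Working it through.** The plan gives no sample-size calculation, effect size, SD, drop-out figure or re-invitation rate, so there is no figure of its own to reproduce. What follows is illustration only.

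**Inputs.** From the documents: up to 30 participants and a 0.05 level (sidedness not stated; two-sided assumed). Assumed: two versions tested in sequence with no true difference, 15 participants first exposed to each, and outcomes N(0,1) with higher better. A participant on version 1 who is asked back fails to return with probability p_w if in the worst 30% and p_r otherwise. A share q is asked back, independently of outcome.

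**Bias formula.** For a standard normal cut at its 30th percentile (z = -0.524, density 0.3477), the lower part has mean -0.3477/0.3 = -1.159 and the upper part 0.3477/0.7 = 0.497. The chance of being a single-version participant is s = 1 - q(1 - p), with p = p_w or p_r. The expected mean of the early single-version group is

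[0.3·s_w·(-1.159) + 0.7·s_r·(0.497)] / [0.3·s_w + 0.7·s_r],

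against 0 for version 2.

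**Results for p_w = 0.5, p_r = 0.1.** False-positive rates are simulated, among runs with at least two people in the early group. The ranges span separate runs, including one that defined the worst 30% by a fixed population cut-off.

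| Share asked back | s_w, s_r | Early-group mean (SD) | False positives |
|---|---|---|---|
| 100% | 0.5, 0.1 | (-0.174 + 0.035)/0.22 = -0.63 | 16 to 18% |
| 75% | 0.625, 0.325 | (-0.217 + 0.113)/0.415 = -0.25 | 7.5 to 9% |
| 50% | 0.75, 0.55 | (-0.261 + 0.191)/0.61 = -0.11 | 5 to 6% |
| 25% | 0.875, 0.775 | (-0.304 + 0.269)/0.805 = -0.04 | about 5% |

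Simulated biases agree: 0.61 to 0.63, 0.25 to 0.26, 0.11 to 0.12, and 0.05 SD.

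**Other return patterns.**

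- 0.8 v 0.1: 0.76 to 0.80 SD and 27 to 31% if all are asked back; 0.19 SD and about 7% if half are.
- 0.6 v 0.2: 0.43 to 0.44 SD and 11 to 13% if all are asked; 0.10 to 0.12 SD and about 6% if half are.
- 0.2 v 0.6 (poor performers more likely to return), all asked: the sign reverses, (0.06·(-1.159) + 0.42·0.497)/0.48 = +0.29 by the formula, 0.26 to 0.29 SD simulated, with about 8% false positives.
- 0.5 v 0.5 (return unrelated to outcome): bias 0, rate 5%.

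A second model, in which leaving depends smoothly on the participant's underlying score, gave the same picture over 5 to 40% withdrawal: 0.49 to 0.95 SD and 16 to 22% with everyone asked back, 0.05 to 0.14 SD and 5 to 6% with half asked back.

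**First exposure instead.** Comparing all 15 first exposed to version 1 with all 15 first exposed to version 2 rejected about 5% of the time in every pattern. It also uses more data. With everyone asked back and 20% non-return unrelated to outcome, the single-version group averages 15 × 0.20 = 3 people. Power for a 1 SD difference is then about a third (33 to 35%), against about 75% with first exposures.

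**The case against.** The strongest reply is that the plan promises no test. Formal analysis is not planned, the rules are contingent, and a within-subject route exists beside this one. That stands, and it sets the severity.

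The next reply concerns a reading that a reader might infer: that early versions will be represented by people who left and later versions by people with no chance to return, so newer versions will look better. The documents do not support it.

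- They do not say that versions follow one another in calendar order, that enrolment is staggered across versions, or that nearly everyone is asked back.
- Return is by invitation, so a single visit can be complete participation.
- A participant who returns but stays on the same version also remains in the set.
- Re-invitation aimed at problems would push the bias the other way.

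The plan also expects low drop-out. With everyone asked back and 10% not returning, the early group averages 15 × 0.10 = 1.5 people. The chance of having at least two is 1 - 0.9^15 - 15·0.1·0.9^14 = 1 - 0.206 - 0.343 = 0.45, so often no test could be run. Low drop-out therefore limits how often the problem arises, but it does not remove the selection when a test is possible.

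Finally, if the completers wording governs, people who withdraw would not be in the set at all. The Withdrawal Criteria text says the opposite, and the conflict is unresolved. Excluding them would still leave a set shaped by who was asked back.

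**Conclusion.** The point holds in a limited form. The single-version set is selected after enrolment, the plan contains routes into it that can depend on outcome, and nothing in the analysis corrects for this. The comparison can therefore be biased, in either direction, and its 5% level is not assured.

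Whether it will be biased, and by how much, cannot be read from the documents. In the illustrations the effect is material only when most participants are asked back and return depends on outcome. It is small when about half are asked back irrespective of outcome, and absent when return is unrelated to outcome. All of these figures rest on the assumed sequence of versions, the 15 v 15 split and the return probabilities.

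The loss of first-exposure data does not depend on outcome-related return; it occurs whenever participants come back on another version.

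Severity is low: one branch of a contingent plan in a non-randomized engineering study with no formal analysis planned. It is worth changing because the change is cheap.

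**What to change.** In Section VII, Trends Analysis, replace the single-version set with wording such as:

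> Between-subjects comparisons of device versions will use each participant's first Helix exposure, whether or not the participant later returns or withdraws. Because version assignment is not randomized, any such test is exploratory.

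Two supporting edits:

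- Reconcile the completers wording in General Considerations with the Withdrawal Criteria text in Section VIII. The proposed rule fits the latter, including its exception for participants who do not want their data used.
- Add to the planned disposition by software version a count, per version, of participants who did not return for reasons other than withdrawal.

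The cost is a few sentences of wording. The comparison needs no new data; the count needs a record of who was not asked back. The downside is that a returning participant's first-exposure record also enters the within-subject tests, so the two results are not independent and should not be presented as separate confirmation. The change removes selection by return only; it does not cure non-random version assignment or any calendar-time difference between versions, hence the exploratory label.
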